mg ponatinib once daily. No large changes in the mean QTc interval (i.e., > 20 ms) from baseline were detected in the study. However, a small increase in the mean QTc interval (i.e., < 10 ms) cannot be excluded because of study design limitations. If a prolongation of QTcF is observed, it is important to perform serum electrolyte analysis (including potassium, calcium, and magnesium) and correct any significant abnormalities with supplements if below normal limits. It is also necessary to review all concomitant medications and discontinue medications that are known or suspected to cause QT prolongation.

If no contributing reason is identified and the reason for QTcF prolongation is believed to be due to ponatinib, dose interruption and reduction guidelines for general non-hematologic toxicities should be followed. Additionally, weekly ECG monitoring is recommended for 4 weeks upon resumption of study drug, then monthly for 6 months, and then every 3 months for the remainder of the study, or more frequently as clinically indicated. Echocardiogram and ECG results for all sites will be reviewed by the lead investigator at *The Ohio State University (OSU)*.

Myelosuppression

Neutropenia, anemia, and thrombocytopenia have all been commonly reported either together or individually in leukemia patients treated with ponatinib. Ponatinib has not been studied in solid tumor patients and whether (or to what extent) myelosuppression will occur in these patients is unknown. While myelosuppression can occur any time during treatment, its onset most commonly occurs within the first month on treatment.

Obtain complete blood counts every 2 weeks for the first 3 months and then monthly or as clinically indicated, and adjust the dose as recommended.

In AP24534-10-201, grade 3 or 4 myelosuppression, reported as an AE, occurred in 52% (262/449) of patients treated with ponatinib. The most commonly reported grade 3/4 myelosuppression AEs were platelet count decrease (43.9%), neutrophil count decrease (24.9%), febrile neutropenia (5.1%) and anemia (22.3%). The incidence of these events was greater in patients with advanced disease than in patients with CP-CML and patients frequently experienced multiple occurrences of these events.. SAEs of myelosuppression events occurred in 10% of patients, with febrile neutropenia and decreased platelet count the 2 most common SAEs, in 3% of patients each. In AP24534-10-201, decreased platelet count led to the discontinuation of 17 patients, making it the most common AE leading to discontinuation. Most patients who experienced grade 3 or 4 decreased platelet count had their first occurrence within the first 3 months of treatment. Most patients recovered from decreased platelet counts with dose interruptions or reductions or with no change to the regimen.

In AP24534-07-101, the incidences of AEs of myelosuppression were similar overall, with incidences of SAEs of febrile neutropenia and decreased platelet count were slightly higher, in 15% and 5% of patients, respectively. Myelosuppression events were reported as SAEs in the expanded access program.

Compromised Wound Healing and Gastrointestinal Perforation

Based on the mechanism of action, ponatinib could potentially compromise wound healing.

Interrupt ponatinib for at least 1 week prior to major surgery. The decision when to resume ponatinib after surgery should be based on clinical judgment of adequate wound healing. Serious GI perforation (fistula) was observed in one patient 38 days post-cholecystectomy in AP24534-10-201. No formal studies of the effect of ponatinib on wound healing have been conducted.

Tumor Lysis Syndrome

Two patients (<1%) treated with ponatinib in AP24534-10-201 developed serious tumor lysis syndrome (TLS). Both cases occurred in patients with advanced CML. Hyperuricemia occurred in 7% (304/449) of patients; the majority had CP CML (19 patients). TLS is likely specific to patients with CML and is unlikely in the solid tumor patients.

Constitutional Symptoms/Joint Pain

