2.2 Investigational New Drug

2.2.1 Ponatinib (AP24534)

Ponatinib (Takeda Pharmaceutical Company; Iclusig) is a FDA-approved oral drug for the treatment of adult patients with T315I-positive chronic myeloid leukemia (CML) (chronic phase, accelerated phase, or blast phase) or T315I-Philadelphia chromosome positive acute lymphoblastic leukemia (Ph+ ALL). It is also indicated in the treatment of adult patients with chronic phase, accelerated phase, or blast phase CML or Ph+ ALL for whom no other tyrosine kinase inhibitor (TKI) therapy is indicated.²⁵ In addition to BCR-ABL, it has activity against FGFR, KIT, platelet-derived growth factor receptor (PDGFR), RET and FLT3 kinases.^{17, 26}

The following information is summarized from the Ponatinib Investigator's Brochure (4.2014) and USPI (12.2013).

Mechanism of Action

AP24534 (international non-proprietary name [INN]: ponatinib) is a novel, orally-available TKI. In addition to BCR-ABL, ponatinib is also a potent inhibitor of members of the FGFR family, which are implicated in a variety of solid tumors. Ponatinib also inhibits other kinases, including KIT, RET, VEGFR, PDGFR α , FMS-like tyrosine kinase 3 (FLT3) receptor tyrosine kinase expressed on vascular endothelium (TIE2), and tyrosine kinase homologous to the Rous sarcoma virus oncogene protein PP60 (SRC). Taken together, the kinase inhibition profile of ponatinib suggests the potential for clinical activity in other hematologic and non-hematologic malignancies in addition to CML.

Preclinical data:

FGFR

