In AP24534-10-201, venous thromboembolic events were observed in 5% (23/449) of ponatinib-treated patients, including deep venous thrombosis/venous embolism/venous thrombosis (11 patients), pulmonary embolism (6 patients), superficial thrombophlebitis (3 patients), retinal vein thrombosis (2 patients) and 1 case each of portal vein thrombosis, and veno-occlusive liver disease. Consider dose interruption of ponatinib in patients who develop serious venous thromboembolism.

Neuropathy

Similar to vascular occlusion, a prospectively defined, MedDRA-based search strategy, containing nearly 300 preferred terms, was employed in the summarization of neuropathy events. Events were further classified as peripheral or cranial neuropathy.

Peripheral and cranial neuropathy has occurred in ponatinib-treated patients. Monitor patients for symptoms of neuropathy, such as hypoesthesia, hyperesthesia, paresthesia, discomfort, a burning sensation, neuropathic pain or weakness. Consider interrupting ponatinib and evaluate if

suspected.

In AP24534-10-201, neuropathy events were observed in 14% (65/449) of patients (cranial in 1% (6/449) and peripheral in 13% (59/449). The most common events were peripheral neuropathy (4%), paresthesia (4%), hypoesthesia (2%), and hyperesthesia (1%). Of the patients who developed neuropathy, 31% (20/65) developed neuropathy during the first month of treatment. One patient discontinued therapy because of neuropathy events (IVth nerve paralysis).

Hepatotoxicity

Liver function test abnormalities are seen with ponatinib, and hepatic failure has been reported. Hepatotoxicity, most commonly manifested by reversible transaminase and alkaline phosphatase elevation and hyperbilirubinemia, has been observed in patients taking ponatinib. Fulminant hepatic failure leading to death occurred in a patient within one week of starting ponatinib. Two additional fatal cases of acute liver failure also occurred. The fatal cases occurred in patients with blast phase CML or Ph+ ALL. Severe hepatotoxicity occurred in all disease cohorts.

Monitor liver function tests at baseline, then at least monthly or as clinically indicated. Interrupt, reduce or discontinue ponatinib as clinically indicated.

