Check serum lipase every 2 weeks for the first 2 months and then monthly thereafter or as clinically indicated. Consider additional serum lipase monitoring in patients with a history of pancreatitis or alcohol use. In patients with pancreatitis, do not consider restarting ponatinib until patients have complete resolution of symptoms and lipase levels are less than $1.5 \times$ ULN.

In AP24534-10-201, treatment-emergent pancreatitis occurred in 7% (30/449) of patients (25; 5.6% Grade 3). Pancreatitis resulted in treatment interruption or dose reduction in 6% of patients (26/449). One patient discontinued ponatinib permanently due to pancreatitis. Twenty-three of 29 patients with pancreatitis had resolution of the events within 2 weeks with dose interruption or reduction or with no change in dose; 2 patients had resolution within 4 days with the dose unchanged. The incidence of treatment-emergent lipase elevation was 41% (grade 3 or 4: 18%). Pancreatitis was the DLT from AP24534-07-101 and has been reported in the expanded access program.

Hemorrhage

Hemorrhagic events have been reported with ponatinib (mostly in leukemic patients with grade 4 thrombocytopenia).

Treatment-emergent hemorrhagic events occurred in 25.6% (115/449) of patients, the majority (87, 19.4%) of which were grade 1/2. The most common hemorrhagic events were epistaxis (7.1%), petechiae (3.1%), and ecchymosis (2.2%).

In AP24534-10-201, serious bleeding events were observed in 5.8% (26/449) of patients treated with ponatinib, including 5 fatalities (1 event each of subdural hematoma, traumatic intracranial hemorrhage, hemorrhagic gastritis, intracranial hemorrhage, and hemorrhagic cerebral infarction. One fatality (hemorrhagic gastritis) was assessed by the investigator as possibly related to ponatinib. The incidence of serious bleeding events was higher in patients with accelerated phase-CML, blast phase-CML, and Ph⁺ALL. The most commonly reported serious bleeding events included: gastrointestinal hemorrhage, subdural hematoma (3 patients each, 0.7%); cerebral hemorrhage, hemorrhoidal hemorrhage, retroperitoneal hematoma, epistaxis, post-procedural hemorrhage, traumatic intracranial hemorrhage, gastric hemorrhage (2 patients each, 0.4%). Three patients had their doses reduced or interrupted due to single events each of ear hemorrhage, gingival bleeding, and subarachnoid hemorrhage. Two patients had study drug

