Grade 4 Sight-threatening consequences; urgent intervention indicated; blindness (20/200 or worse).	
 Consult ophthalmologist immediately. Exclude ME and RVO. Continue follow up examination(s) (by retinal specialist if available) for ME and RVO. 	Permanently discontinue ponatinib.

ME = macular edema; RVO = retinal vein occlusion; RH = retinal haemorrhage. SAE = serious adverse event
 * If visual changes are clearly unrelated to study treatment (e.g., allergic conjunctivitis), monitor closely but ophthalmic examination is not required.
 * If ocular toxicities do not resolve within 14 days, permanently discontinue ponatinib.

Dose modification for neuropathy

CTCAE Grade	Action and Dose Modification
Grade 1 or transient Grade 2	No intervention
Grade 2 lasting \geq 7 days	
Hold ponatinib Resume at 45 mg after recovery to \leq grade 1
 
Recurrence at 45 mg: Hold ponatinib Resume at 30 mg after recovery to \leq grade 1
 
Recurrence at 30 mg: Hold ponatinib Resume at 15 mg after recovery to \leq grade 1
 
Recurrence at 15 mg: Discontinue ponatinib

Grade 3 or 4	
Hold ponatinib Resume at 30 mg after recovery to \leq grade 1
 
Recurrence at 30 mg: Hold ponatinib Resume at 15 mg after recovery to \leq grade 1
 
Recurrence at 15 mg: Discontinue ponatinib

Dose Modifications for reduced left ventricular ejection fraction (LVEF).

Severe congestive heart failure (CHF) and left ventricular (LV) dysfunction have been reported in patients taking ponatinib. Patients should be monitored carefully for signs or symptoms consistent with cardiac failure. ECHOs must be performed at regular intervals as outlined in the Study Calendar. The same procedure (either ECHO or MUGA, although ECHO is preferred) should be performed at baseline and at follow-up visit(s). Consider discontinuation of ponatinib in patients who develop serious CHF.

Symptoms	LVEF-drop (%) or CTCAE grade	Action and Dose Modification

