10. STUDY CALENDAR

Baseline evaluation must be conducted within 2 weeks prior to start of ponatinib therapy. Imaging studies must be done \leq 4 weeks prior to the start of therapy. In the event that the patient's condition is deteriorating, laboratory evaluations should be repeated within 48 hours prior to initiation of the next cycle of therapy. Appropriate delays in study treatment or procedures are allowed to adjust for holidays or weekends. Each cycle is **28** days.

Study Assessment ^{s¹}	Screen	During Ponatinib Therapy		Final Study Visit ³	Follow-Up ⁹
Informed Consent	X				
Baseline Demographics	X				
Ophthalmic Exam ²	X	As clinically indicated			
Medical History / Interim History	X	Day 1 (\pm 3 days) of each cycle		X	
Concomitant Medications	X	Continuous			
Physical Exam	X	Day 1 (\pm 3 days) of each cycle		X	
ECOG Performance Status	X	Day 1 (\pm 3 days) of each cycle		X	
Vital Signs (BP, HR, Temperature, weight)	X	Day 1 (\pm 3 days) of each cycle		X	
Blood Pressure (at home) ⁴		Twice per week during cycle			
Chemistry ⁵	X	Day 1 (\pm 3 days) of each cycle		X	
Triglycerides	X				
CBC, Diff, Plt	X	Every 2 weeks for first 2 cycles	Day 1 (\pm 3 days) from cycle 3		
Liver Function Testing		Cycle 1 Day 1	Once per month, or more frequent if clinically indicated		
Serum Amylase, Serum Lipase	X	Every 2 weeks for first 2 cycles	Day 1 (\pm 3 days) from cycle 3		
Pregnancy Test ⁶	X				
12-Lead ECG	X	Repeated as Clinically Indicated			
LVEF (ECHO)	X	Repeated every 3 cycles \pm 7 days or as Clinically Indicated			
Research Biopsy(s) ⁷	Research biopsies on eligible	Research biopsies will be attempted on all patients at time of progression			

	patients prior to the study			
Study Agents		Ponatinib will be administered daily		
Tumor measurement S ⁸	X	Staging will occur after every 2 cycles \pm 7 days or as Clinically Indicated		
Adverse Events		Continuous		

1. Assessments scheduled on days of dosing must be done prior to administration of study drug(s), unless otherwise specified.
2. Ophthalmic exam will include indirect and direct fundoscopy, visual acuity, visual field examination, tonometry and color fundus photos. Additional ophthalmic exams will be performed if symptomatically warranted.
3. Final Study Visit must occur 21 days (\pm 7 days) after last dose of study drug.
4. Blood pressure cuff will be provided by Takeda. Patients will record readings in diary (Appendix B) and bring with them to clinic visits.

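### The Study Calendar ends two-weekly blood counts after 2 cycles, but the protocol's safety text asks for 3 months, so the cycle 3 day 15 count is dropped

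*Combined protocol and SAP*

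**What the plan says.** Two parts of the protocol set the frequency of complete blood counts.

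- **Section 2.2.1, Myelosuppression:** "Obtain complete blood counts every 2 weeks for the first 3 months and then monthly or as clinically indicated". Section 2.2.1 opens by stating its source: "The following information is summarized from the Ponatinib" Investigator's Brochure and the US label.
- **Section 10, Study Calendar, CBC/Diff/Plt row:** "Every 2 weeks for first 2 cycles", then Day 1 (±3 days) from cycle 3. Cycles last 28 days.

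The myelosuppression table in Section 6.1 sets the action thresholds but gives no frequency for counts.

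The other two blood-test schedules in Section 2.2.1 agree with their calendar rows. For lipase the safety text says "Check serum lipase every 2 weeks for the first 2 months and then monthly thereafter or as clinically indicated", and the calendar's amylase/lipase row covers 2 cycles. For liver tests it says "Monitor liver function tests at baseline, then at least monthly or as clinically indicated", and the calendar says "Once per month, or more frequent if clinically indicated".

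**The concern.** The calendar asks for less monitoring than the safety text, and sites are likely to work from the calendar. Section 6.1 itself points there for cardiac imaging: "ECHOs must be performed at regular intervals as outlined in the Study Calendar". The blood-count row carries the same wording as the amylase/lipase row, where 2 cycles is right. This suggests an oversight but does not prove one.

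The dropped count lies in a period that the protocol singles out. On platelets, Section 2.2.1 reports: "Most patients who experienced grade 3 or 4 decreased platelet count had their first occurrence within the first 3 months of treatment". Two rules depend on these counts: ponatinib is interrupted when ANC is below 1 x 10^9/L or platelets are below 50 x 10^9/L (Section 6.1), and aspirin is held at platelets of 75,000 or below (Section 5.1). Section 3.1.12 admits patients with platelets of exactly 75,000, already at the aspirin-hold level. With no count on day 71, a fall without symptoms could go unseen while both drugs continue.

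**Working it through.** **Inputs.** Cycle length 28 days and the blood-count row (Section 10). Two-weekly counts for 3 months (Section 2.2.1). Cohort sizes of 30 and up to 15 (Section 12.3). The two-weekly series is taken to start on cycle 1 day 1.

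**Day count.** Day = 28 x (cycle - 1) + day of cycle.

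| Schedule | Count days through day 85 | Number |
|---|---|---|
| Section 2.2.1 | 1, 15, 29, 43, 57, 71, 85 | 7 |
| Study Calendar | 1, 15, 29, 43, 57, 85 | 6 |

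The missing count is cycle 3 day 15: 28 x 2 + 15 = day 71. Reading 3 months as anything from 84 to 92 days gives the same answer. Day 85 is on the calendar anyway as cycle 4 day 1, and the next two-weekly count would be day 99.

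**Gap.** The nominal gap is 85 - 57 = 28 days instead of 71 - 57 = 14. With the ±3-day windows it can reach (85 + 3) - (57 - 3) = 34 days.

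**Delay in detection.** A fall that crosses a threshold after day 57 and by day 71 would be found on day 71 under the safety text and on day 85 under the calendar, at most 85 - 71 = 14 days later. A fall after day 71 would be found on day 85 under both.

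**Existing safeguards.** Section 10 asks for repeat laboratory tests in a deteriorating patient within 48 hours before the next cycle. That falls near day 85, so it does not supply a day 71 count. Section 2.2.1 provides for extra counts when clinically indicated, and the calendar does not forbid them, but they would not catch a fall without symptoms.

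**Number of patients.** The documents do not say what share of falls occurs in any given interval, so late-detected events cannot be sized. The figures below are assumed ranges for platelet falls at any time on treatment among 30 + 15 = 45 patients:

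- **GIST study, any grade.** Platelet decrease is not among the listed events, and all unlisted events were below 10%: fewer than 45 x 0.10 = 4.5.
- **GIST study, grade 3 or 4.** There were no grade 4 events, and platelet decrease is not among the grade 3 events seen in more than one patient. That means at most 1 of 35 (19 / 0.543 = 35 patients), and 45 x 1/35 = 1.3.
- **Leukemia phase 2 study, grade 3 or 4.** The rate was 43.9%: 45 x 0.439 = 19.8.

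On a like-for-like grade 3 or 4 basis the range is therefore about 1 to 20. Only those falling between days 57 and 71, in patients still on treatment, would be affected.

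**The case against.** The strongest reply is that Section 2.2.1 is background taken from the brochure and label, based on leukemia patients, while Section 10 is the schedule for this trial. The Safety Profile text also suggests that some adverse effects, with neutropenia as an example, may be specific to myeloproliferative disorders, so a lighter schedule in solid tumors could be deliberate. Other background guidance is relaxed later: periodic eye examinations in Section 2.2.1 become examinations at baseline and when clinically warranted in Section 6.1.

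This stands in part. A deliberate choice is possible, and the protocol contains a remark that could support one. But that remark is not tied to the calendar, and the Myelosuppression text says the extent of the problem in solid-tumor patients is unknown. Section 2.2.1 is also more than background. It contains instructions for this trial, such as twice-weekly home blood pressure and lead-investigator review of ECG and echocardiogram results from all sites.

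A second reply is that most events within 3 months is a cumulative statement. It is compatible with nearly all falls occurring by day 56, and Section 2.2.1 says onset is most common in the first month, which the calendar covers every 2 weeks. This is right, and it is why the point is minor.

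A third reply is that a patient already held for low counts needs further counts to meet the recovery criteria in Section 6.1. This is also right. The exposure is limited to a new, silent fall in cycle 3.

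**Conclusion.** The point holds as a low-severity inconsistency in safety monitoring. The two schedules conflict, and the calendar omits exactly one count, day 71, for each patient still on treatment in cycle 3. The consequence is a nominal 28-day gap instead of 14 and up to 14 days' later detection of a silent fall that should stop ponatinib or aspirin.

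The mismatch and the day count are certain. That sites follow the calendar, and that the shorter row is an oversight, are inferences. The number of patients who would be affected is unknown and could be close to zero. The primary endpoint, sample size and error rates are not touched.

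**What to change.** In the Section 10 Study Calendar, change the CBC/Diff/Plt row to every 2 weeks for the first 3 cycles, then Day 1 (±3 days) from cycle 4, and add that counts may also be done when clinically indicated. Leave the amylase/lipase row alone, because it already matches its safety text.

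The cost is one routine blood draw per patient still on treatment at cycle 3 day 15, at most 30 + 15 = 45 in the whole trial. The actual number would be lower, since patients who progress at the first staging, after 2 cycles, stop before day 71.

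Shortening the Section 2.2.1 text to 2 months would also remove the conflict, but it keeps the 28-day gap. It should be chosen only with a stated reason why solid-tumor patients need fewer counts.

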Based on its mechanism of action and findings in animals, ponatinib can cause fetal harm when administered to a pregnant woman. Ponatinib was studied for effects on embryo-fetal development in pregnant rats given oral doses of 0.3, 1, and 3 mg/kg/day during organogenesis. At the maternally toxic dose of 3 mg/kg/day (equivalent to the AUC in patients receiving the recommended dose of 45 mg/day), ponatinib caused embryo-fetal toxicity as shown by increased resorptions, reduced body weight, external alterations, multiple soft tissue and skeletal alterations, and reduced ossification. Embryo-fetal toxicities also were observed at 1 mg/kg/day (approximately 24% the AUC in patients receiving the recommended dose) and involved multiple fetal soft tissue and skeletal alterations, including reduced ossification. There are no adequate and well-controlled studies with ponatinib in pregnant women. Advise women to avoid becoming pregnant while taking ponatinib. If this drug is used during pregnancy, or if the patient becomes pregnant while taking this drug, the patient should be apprised of the potential hazard to a fetus.

Pediatric Use

The safety and efficacy of ponatinib in patients less than 18 years of age have not been established.

Nursing

It is unknown whether ponatinib is excreted in human milk. Because of the potential for serious adverse reactions in nursing infants from ponatinib, a decision should be made whether to discontinue nursing or to discontinue ponatinib, taking into account the importance of the drug to the mother.

Geriatric use

One hundred and fifty-five of 449 patients (35%) in the CML clinical trial of ponatinib were 65 years of age and over. Forty-six percent of patients \geq 65 years had vascular occlusion events. Patients of age \geq 65 years are more likely to experience adverse reactions including vascular occlusion, decreased platelet count, peripheral edema, increased lipase, dyspnea, asthenia, muscle spasms, and decreased appetite. In general, dose selection for an elderly patient should be cautious, reflecting the greater frequency of decreased hepatic, renal, or cardiac function, and of concomitant disease or other drug therapy.

Hepatic Impairment

The Mass-Balance study (AP24534-11-104) confirmed that ponatinib elimination in humans primarily occurs via the liver. AP24534-12-109, Phase-1 study compared the PK of 30-mg ponatinib in subjects with chronic hepatic impairment with those of matched healthy subjects. The study was designed as open-label, single-dose, parallel-group, and nonrandomized. Eighteen subjects with hepatic impairment (6 each in Child-Pugh categories A, B, and C, corresponding to mild, moderate, and severe impairment, respectively) were matched to 9 healthy subjects. The study demonstrated that ponatinib or metabolite AP24600 exposure appeared to be comparable, albeit slightly higher, in subjects with mild hepatic impairment (Child-Pugh A) compared to healthy subjects. In contrast, lower plasma exposures of ponatinib and AP24600 were observed in subjects with either moderate or severe hepatic impairment (Child-Pugh B and C),

respectively) relative to healthy control subjects. PK data alone do not suggest the need for a starting dose adjustment for ponatinib in subjects with varying degrees of hepatic impairment. No clinically meaningful differences were observed in ponatinib PK in subjects with chronic hepatic impairment compared to matched healthy subjects. Ponatinib should be used with caution in patients with moderate or severe hepatic impairment.

Renal Impairment

Although renal excretion is not a major route of elimination, ponatinib has not been studied in patients with renal impairment. The potential for moderate or severe renal impairment to affect hepatic elimination has not been determined.

